10.6 Required Routine Reporting

10.61 Baseline and Adverse Events Evaluations

Pretreatment symptoms/conditions to be graded at baseline and adverse events to be graded at each evaluation per CTCAE v4.0 grading **unless** otherwise stated in the table below:

| System Organ Class (SOC) | Adverse event/Symptoms | Baseline | Each evaluation |
|--------------------------------------|---------------------------|----------|-----------------|
| Investigations | Platelet count decreased* | X | X |
| Blood and lymphatic system disorders | Anemia* | X | X |

*** Grading will be performed by the study statisticians at the time of analysis based on the CLL toxicity grading scale for blood counts in Appendix V. Anemia grade per CTCAE will also be recorded for reporting purposes.**

10.62 Submit via appropriate MCCC Case Report Forms (i.e., paper or electronic, as applicable) the following AEs experienced by a patient and not specified in Section 10.6:

10.621 Grade 2 AEs deemed *possibly, probably, or definitely* related to the study treatment or procedure.

10.622 Grade 3 and 4 AEs regardless of attribution to the study treatment or procedure.

10.623 Grade 5 AEs (Deaths)

10.6231 Any death within 30 days of the patient's last study treatment or procedure regardless of attribution to the study treatment or procedure.

10.6232 Any death more than 30 days after the patient's last study treatment or procedure that is felt to be at least possibly treatment related must also be submitted as a Grade 5 AE, with a CTCAE type and attribution assigned.

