- 16.323 Time to requirement of next therapy: A landmark analysis will be conducted to evaluate time to requirement of next therapy for patients who achieve a confirmed MRD-negative response in both the blood and bone marrow vs. those who remain MRD-positive, as assessed at 48 weeks (end of 12 cycles; +/- 4 weeks). Patients who discontinue treatment before 48 weeks are excluded from this analysis. Time to requirement of next therapy will be defined as the time from the 48 week MRD evaluation until the time of initiation of subsequent treatment for progressive CLL. The distribution of time to requirement of next therapy will be estimated using the Kaplan-Meier method and log-rank statistics will be utilized to evaluate differences between the two groups.
- 16.324 Progression-free survival: A landmark analysis will be conducted to evaluate progression-free survival for patients who achieve a confirmed

MRD-negative response in both the blood and bone marrow vs. those who remain MRD-positive, as assessed at 48 weeks (end of 12 cycles; +/- 4 weeks). Patients who discontinue treatment before 48 weeks are excluded from this analysis. Progression-free survival will be defined as the time from the 48 week MRD evaluation until the time of disease progression per the IWCLL criteria or death due to any cause. The distribution of progression-free survival will be estimated using the Kaplan-Meier method and log-rank statistics will be utilized to evaluate differences between the two groups.

16.325 Adverse Events: Platelets and hemoglobin will be graded according to the Grading Scale for Hematologic Adverse Events in CLL Studies in Appendix V. The maximum grade for each type of adverse event, regardless of causality, will be recorded and reported for each patient, and frequency tables will be reviewed to determine adverse event patterns. Adverse events will continue to be recorded and reported up to 30 days after the last day of study drug treatment.

16.33 Correlative Analyses. The reports on the correlative will be descriptive as they are exploratory in nature.

16.332 Study of the impact of ibrutinib treatment on mood is exploratory in nature. Reports of these correlative analyses will be descriptive.

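### Section 16.325 plans an all-cause maximum-grade summary with no grade floor, but below grade 3 the reporting rules in 10.62 do not require all-cause data for most event types

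*Combined protocol and SAP*

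**What the plan says.** Section 16.325 describes the adverse event analysis. Platelets and hemoglobin are graded by Appendix V. For everything else the rule is: "The maximum grade for each type of adverse event, regardless of causality, will be recorded and reported for each patient". The section adds that "frequency tables will be reviewed to determine adverse event patterns", and gives the time window: "Adverse events will continue to be recorded and reported up to 30 days after the last day of study drug treatment". It names no minimum grade.

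Section 10.62 lists what must go on the case report forms for events not already covered in 10.6:

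- 10.621, with an attribution filter: "Grade 2 AEs deemed *possibly, probably, or definitely* related to the study treatment or procedure".
- 10.622, without such a filter: "Grade 3 and 4 AEs regardless of attribution to the study treatment or procedure".
- 10.6231: deaths within 30 days of the "last study treatment or procedure regardless of attribution to the study treatment or procedure".
- 10.6232: a later death "that is felt to be at least possibly treatment related must also be submitted as a Grade 5 AE".

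Grade 1 does not appear in the list. The table in 10.61 covers two terms at baseline and at each evaluation, platelet count decreased and anemia. Its note says: "Grading will be performed by the study statisticians at the time of analysis based on the CLL toxicity grading scale".

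**The concern.** One section promises a summary without regard to cause. The other collects grade 2 with an attribution filter and does not ask for grade 1. If both are followed as written, the frequency tables for most event types mix three rules: all-cause from grade 3 up, related-only at grade 2, and whatever happens to be submitted at grade 1.

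The toxicity profile of maintenance ibrutinib is a secondary goal (2.22). Patients are in response after induction and may take the drug for up to 36 cycles (7.1), so low-grade toxicity is a real part of that profile. What is at stake is how the low-grade results are described, and whether a count that depends partly on investigator attribution is presented as an all-cause count.

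**Working it through.** The plan gives no figure on this point, so the check is a comparison of texts. For event types with no special route, within 30 days of the last study drug:

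| Maximum grade | Promised in 16.325 | Required by 10.62 | All-cause label supported? |
|---|---|---|---|
| 1 | Any cause | Not listed | No |
| 2 | Any cause | Only if at least possibly related (10.621) | No |
| 3 and 4 | Any cause | Any cause (10.622) | Yes |
| 5 | Any cause | Any cause (10.6231) | Yes |

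Deaths under 10.6232 fall outside the 16.325 window and do not bear on the low-grade mismatch.

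The next step is whether another provision fills the two gaps.

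1. **Platelets and hemoglobin.** 10.61 and Appendix V grade both at every evaluation with no attribution filter. The gap is closed for these two. Neutrophils are not in the 10.61 table, so low-grade neutrophil decreases stay under 10.62.
2. **Serious events.** 10.4 requires them whatever their attribution, and 10.1 item f sends every expedited report into the routine data as well. The gap is closed for serious events below grade 3.
3. **Special-interest bleeding.** 10.41 covers central nervous system hemorrhage of any grade and serious bleeding of any grade, without regard to attribution. The gap is closed for these, provided the reports reach the study data under 10.1 item f.
4. **Second malignancies.** 10.54 requires routine reporting.
5. **Form schedule.** Footnote 20 in Section 4.0 makes adverse event forms due every 28 days, and 18.1 lists a Nadir/Adverse Event form. Both say when a form is due. Neither says which grades or attributions must be entered on it.

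What remains without an all-cause requirement is the ordinary, non-serious grade 1 event and the ordinary, non-serious grade 2 event judged unlikely or unrelated.

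Last, what depends on those events:

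- The 16.352 rule counts non-hematologic events of grade 4 or higher that are at least possibly related. 10.622 and 10.623 require these, so the rule is unaffected.
- The 16.211 rule counts confirmed MRD-negative responses and uses no adverse event data.
- Frequencies at grade 3 or higher rest on rules that agree.

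**The case against.** The strongest reply is that 16.325 governs analysis and 10.62 governs collection. On that reading, ignoring causality means only that the analyst must not filter the events that were recorded, and this can be done in full on whatever 10.62 brings in. The documents contain no table shells or titles, so no wrong label yet exists. The first part does not remove the problem. The sentence in 16.325 covers recording as well as reporting, so read as a collection instruction it contradicts 10.62. Read as analysis only, its output below grade 3 is still not all-cause for most event types. It is true that the label is prospective, which is why a wording change is enough.

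A second reply is that 10.62 is a minimum, that sites may submit more, and that the forms are not in the documents. This stands, and it is why no loss can be claimed. It does not rescue the all-cause description, because extra submissions would make low-grade counts depend on local practice.

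A third reply is that a footnote would do. This is partly right: the explanatory sentence carries most of the correction. A footnote alone would leave the body of 16.325 promising something different.

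A reader might go further and infer a measurable understatement from the Background, where for example diarrhea is 42.1% overall and 30.2% when considered related (1.2 (C), Safety). The documents do not support that step. Those rates pool all grades, come from other ibrutinib monotherapy studies, do not split grades 1 and 2 by attribution, and say nothing about what sites here will submit. Nor does any section plan to compare this trial's adverse event rates with the Background, so no flawed comparison can be charged to the plan.

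**Conclusion.** The two sections disagree below grade 3, and only there. Apart from platelets and hemoglobin, serious events, special-interest bleeding events and second malignancies, the required data support an all-cause summary only at grade 3 or higher. The size of any understatement at grades 1 and 2 cannot be derived from the documents, and it may be zero.

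A reader might infer that safety monitoring or the trial's conclusion is weakened. It is not: the stopping rule, the decision rule and the results at grade 3 or higher are untouched.

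The conclusion assumes that 10.62 is the operative submission rule and that forms not shown do not widen it. If they require all grades whatever the cause, the two sections should still be aligned in the text. This is a minor correction to the description of a secondary safety summary. The mismatch in the text is clear; its practical effect is unknown.

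**What to change.** Reword 16.325 to report, per treated patient and event type, up to 30 days after the last study drug:

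- (a) maximum grade 3 or higher, whatever the cause;
- (b) maximum grade 2 or higher, at least possibly related;
- (c) platelets and hemoglobin at all grades by Appendix V, as already planned;
- (d) serious events and special-interest bleeding events at any grade, whatever the cause, tabulated and not only listed.

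Item (d) is needed because these events are required without an attribution filter. Tables (a) to (c) alone would drop some of them below grade 3.

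Add one sentence under the tables: other grade 1 events, and other grade 2 events judged unlikely or unrelated, are not systematically required under 10.62, so the low-grade results are not all-cause rates.

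The cost is one reworded paragraph and the matching table layout. It uses data already required and changes no form, visit or sample size. The downside is that low-grade results carry a narrower label.

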Rash: Rash has been commonly reported in subjects treated with either single agent ibrutinib or in combination with chemotherapy. In a randomized Phase 3 study (PCYC-1112-CA), rash occurred at a higher rate in the ibrutinib arm than in the control arm. Most rashes were mild to moderate in severity. One case of Stevens-Johnson Syndrome (SJS), with a fatal outcome, was reported in a subject with CLL. The subject received ibrutinib (420 mg/day) and was also receiving various antibiotics and antigout medication (allopurinol) known to be associated with SJS.

Cardiac: Atrial fibrillation and atrial flutter have been reported in subjects treated with ibrutinib, particularly in subjects with cardiac risk factors, acute infections, and a previous history of atrial fibrillation. In particular subjects with a history of cardiac arrhythmias should be monitored closely.

Other Malignancies: Other malignancies, most frequently skin cancers, have occurred in subjects treated with ibrutinib. Across the MCL (PCYC-1104-CA) and CLL/SLL studies (PCYC-1112-CA and PCYC-1102-CA), skin cancers and non-skin cancers were reported in 5.0% (18/357) and 2.5% (9/357) of subjects who received ibrutinib, respectively.

Infection: Fatal and non-fatal infections have occurred with ibrutinib therapy. At least 25% of subjects with MCL and 35% of subjects with CLL had Grade 3 or greater infections per NCI Common Terminology Criteria for Adverse Events (CTCAE). The most commonly reported infections include pneumonia, cellulitis, urinary tract infection and sepsis. Isolated cases of JC virus reactivation resulting in progressive multifocal leukoencephalopathy (PML) have been observed and resulted in death. Two cases in relapsed CLL subjects have been reported. One case occurred after multiple prior rituximab regimens and less than one year after the last dose of rituximab and high dose steroid administration. The second case occurred during concomitant administration of rituximab, bendamustine and ibrutinib.

Cytopenias: Treatment-emergent Grade 3 or 4 cytopenias (neutropenia, thrombocytopenia, and anemia) were reported in subjects treated with ibrutinib.

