10.53 Secondary Malignancy

- A **secondary malignancy** is a cancer caused by treatment for a previous malignancy (e.g., treatment with investigational agent/intervention, radiation or chemotherapy). A secondary malignancy is not considered a metastasis of the initial neoplasm.
- All secondary malignancies that occur following treatment with an agent under an IND/IDE will be reported. Three options are available to describe the event:
 - Leukemia secondary to oncology chemotherapy (e.g., Acute Myelocytic Leukemia [AML])
 - Myelodysplastic syndrome (MDS)
 - Treatment-related secondary malignancy
- Any malignancy possibly related to cancer treatment (including AML/MDS) should also be reported via the routine reporting mechanisms outlined in each protocol.

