10.54 Second Malignancy

A second malignancy is one unrelated to the treatment of a prior malignancy (and is NOT a metastasis from the initial malignancy). Second malignancies require ONLY routine reporting unless otherwise specified.

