11.2 Evaluation for Progression of Disease

11.21 **PROGRESSION (PD):** Patients will continue to receive protocol therapy unless they have evidence of disease progression according to the IWCLL criteria⁶ as evidenced by:

11.211 $\geq 50\%$ increase in the sum of the products of at least 2 lymph nodes on 2 consecutive determinations 2 weeks apart (at least one node must be ≥ 2

cm) that persist for > 3 months or the appearance of new palpable lymph nodes >1.5 cm not due to a tumor flare. Enlargements or the appearance of new nodes due to a tumor flare do NOT qualify as progression.

- 11.212 $\geq 50\%$ increase in the size of the liver and/or spleen as determined by measurement below the respective costal margin on 2 consecutive determinations 2 weeks apart and with a minimum of a ≥ 2 cm increase in size from baseline; or appearance of hepatomegaly or splenomegaly which was not previously present at baseline and not due to a tumor flare.
- 11.213 Transformation to a more aggressive histology (e.g. Richter's transformation).

Note: If a patient develops DLBCL at any time, it will be considered disease progression. If the patient develops any other hematologic malignancy while on study, it will not be considered progressive disease.

- 11.214 $\geq 50\%$ increase in the absolute number of circulating lymphocytes NOT due to infection, tumor flare or drug-associated lymphocytosis (taking as reference for progressive disease the smallest absolute lymphocyte count recorded since the treatment started). The absolute lymphocyte count must be at least $5000/\text{mm}^3$ to qualify as disease progression.
- 11.215 In the absence of progression as defined by 1, 2, 3, or 4 above, the presence of a ≥ 2 g/dl decrease in HGB, or $\geq 50\%$ decrease in platelet count or absolute neutrophil count will NOT exclude a patient from continuing the study. Work-up of such decreases to exclude auto-immune hemolytic anemia, pure red cell aplasia, or idiopathic thrombocytopenic purpura (ITP) should be considered.
- 11.216 For patients who achieve a CR or nodular PR, progression will be defined as recurrence of circulating leukemia cell clone and an ALC >5000 or recurrence of adenopathy >1.5 cm not due to a tumor flare.

11.22 **Not PD:** The patient was evaluated for progression only in this cycle and a formal response evaluation did not occur. The patient did not meet the criteria for progression per section 11.21.

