| CRF | Event Monitoring Phase ¹ | | | | |
|------------------|---|--|--|-------|--------------------|
| | q. 3 months until PD or subsequent treatment for CLL ² | At PD or subsequent treatment for CLL ² | q. 6 mos. after PD or subsequent treatment for CLL | Death | New Primary |
| Event Monitoring | X | X | X | X | At each occurrence |

1. If a patient is still alive 5 years after registration, no further follow-up is required.
2. Submit copy of documentation of progression to the Operations Office, Attention: QAS for MC1481, [contact].

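### Section 16.325 closes the safety analysis 30 days after the last dose, so no planned result identifies or counts later second malignancies, although the trial collects them to 5 years

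*Combined protocol and SAP*

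**What the plan says.** Goal 2.22 is the toxicity profile of ibrutinib maintenance. Section 16.325 is its only planned analysis. It builds frequency tables from one summary per patient: "The maximum grade for each type of adverse event, regardless of causality, will be recorded and reported for each patient". It then sets the window: "Adverse events will continue to be recorded and reported up to 30 days after the last day of study drug treatment".

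Other parts of the protocol look further ahead:

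- **Named harm.** Section 1.2 (Safety, Other Malignancies): "Other malignancies, most frequently skin cancers, have occurred in subjects treated with ibrutinib". Across the MCL and CLL/SLL studies cited there, "skin cancers and non-skin cancers were reported in 5.0% (18/357) and 2.5% (9/357) of subjects who received ibrutinib".
- **Case reporting.** Section 10.53: "All secondary malignancies that occur following treatment with an agent under an IND/IDE will be reported". No time limit is attached. Section 10.54 covers cancers unrelated to treatment: "Second malignancies require ONLY routine reporting unless otherwise specified".
- **Observation.** The Section 4.0 schedule includes an adverse event assessment during Observation. The Section 18.1 form table requires the Nadir/Adverse Event form then. Observation can last 2 years (Section 13.2).
- **Event monitoring.** The Section 18.1 table has a New Primary column, to be completed at each occurrence. Its footnote ends follow-up: "If a patient is still alive 5 years after registration, no further follow-up is required".
- **Progression.** Section 11.213 counts transformation and DLBCL as progression, and adds: "If the patient develops any other hematologic malignancy while on study, it will not be considered progressive disease".

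**The concern.** The trial asks for data on a harm that it names itself, then sets an analysis rule that leaves the later part of those data out of the toxicity result. Patients enter in remission after induction and may take ibrutinib for up to 36 cycles. A reader weighing MRD clearance against longer-term cost would want to know how many developed another cancer, including after stopping. Followed as written, Section 16.325 would not say.

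The gap is widest for patients who stop early. Those who stop for progression, adverse events or refusal go directly to event monitoring (Section 13.1), where the only scheduled form is the Event Monitoring form. For them the New Primary entry is the scheduled source of later cancers, and no analysis draws on it.

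**Working it through.** **1. The plan's own figures.** The plan gives no figure for the safety window. The one computable design figure is the binomial rule (n = 32, at least 4 successes). Exact tails at true rates 0.05, 0.10, 0.15 and 0.20 are 0.0738, 0.3997, 0.7279 and 0.9069, which match the stated 0.07, 0.40, 0.73 and 0.91. This point changes none of them.

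**2. Length of the window.** Inputs: 28-day cycles, at most 36 (Section 7.1); close at 30 days after last dose (16.325); follow-up to 5 years (18.1), taken as 5 × 365.25 = 1826 days.

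Days outside = 1826 − (cycles × 28 + 30).

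| Cycles taken | Window closes (day) | Days outside | Share of 5 years |
|---|---|---|---|
| 36 | 1008 + 30 = 1038 | 788 | 43% |
| 12 | 336 + 30 = 366 | 1460 | 80% |
| 6 | 168 + 30 = 198 | 1628 | 89% |
| 1 | 28 + 30 = 58 | 1768 | 97% |

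For the completer, in months: 1038 / 30.44 = 34.1, and 60 − 34.1 = 25.9. This assumes no held cycles, survival to 5 years, and first dose on the day of registration. Treatment may start up to 14 days after registration (Section 6.7), which shortens the time outside by at most that much. Holds or a prolonged last cycle would shorten it further.

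**3. The same window at the earliest analysis.** Section 16.23 lets the final analysis begin about 2.5 years after the trial opens. Thirty months is 30 × 30.44 = 913 days, less than the 1008 days needed for 36 cycles. No one can have completed treatment by then, so only early stoppers have follow-up outside the window. For a patient registered at the start who stopped after 12 cycles, that is 30 − 366/30.44 = 18.0 months.

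**4. Where a malignancy after day 30 could surface.**

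| Route | What it captures | Planned result that counts second cancers? |
|---|---|---|
| 16.325 tables | Events to day 30 | Not after day 30, as written |
| 16.324 landmark PFS | DLBCL/transformation as progression, death from any cause; excludes patients who stop before 48 weeks | No; not identified as second cancers |
| 16.323 time to next therapy | Start of treatment for progressive CLL; same exclusion | No |
| 10.53, 10.54, 10.6232, 10.7 | Case reporting, related late deaths, late-event forms | No analysis named |
| 16.351, 16.352 | Quarterly and DSMB review; rule on related grade 4 or higher non-hematologic events | Monitoring, not a result |
| 18.1 New Primary | Every new primary to 5 years | No analysis named |

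**5. Number of cases.** The cited counts give at most (18 + 9)/357 = 7.56%, if no patient had both types. For 35 patients, 35 × 0.0756 = 2.65 expected and 1 − (1 − 0.0756)^35 = 0.94 chance of at least one. That covers a malignancy at any time, inside or outside the window. The follow-up behind the 357 is not given there, so the split cannot be worked out.

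As an illustration only, with an assumed rate of 1% to 3% per year (not from the documents) and 32 patients each with 788 days (2.16 years) outside: 32 × 0.01 × 2.16 = 0.7 to 32 × 0.03 × 2.16 = 2.1 cases.

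**The case against.** The strongest reply is that late cancers are not lost. Fatal ones enter the landmark PFS, DLBCL and Richter's transformation are progression, late related deaths are submitted as Grade 5 events, and Sections 10.53 and 10.54 send malignancies to case reporting. Adverse event forms are due in Observation, so some late cancers may reach the data that Section 16.325 tabulates. This stands in part: a reader might infer that late cancers vanish from the trial, and the documents do not support that. But none of these routes yields a planned count, and the landmark analyses drop everyone who stopped before 48 weeks.

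Second, a 30-day window is a reasonable description of on-treatment toxicity, and final analysis may begin at about 30 months. That also stands. A reader might take the 43% as the share of safety follow-up missing from the final analysis; it applies only to an analysis after full 5-year follow-up, for which the plan sets no date.

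Third, with about 35 patients, no control arm, prior induction in everyone, and follow-up that continues after further CLL therapy, a late cancer cannot be attributed to ibrutinib. The cited rates come partly from relapsed or refractory MCL and CLL, and two-thirds of the cases (18/27) were skin cancers. This rules out any causal claim and makes a competing-risk curve unnecessary. It does not argue against a descriptive count.

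Finally, a reader might infer that PFS is defective because other hematologic cancers are not progression. It is not: they are not CLL progression. The rule only confirms that PFS does not fill the gap.

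**Conclusion.** The point holds as a reporting gap that should be closed. No planned result identifies or counts a second malignancy diagnosed more than 30 days after the last dose, although the protocol names the harm and collects the data. The 30-day sentence is also unreconciled with the adverse event forms due in Observation.

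The time outside the window is 43% of 5 years for an uninterrupted 36-cycle completer and 80% to 97% for stops after 12 cycles down to 1, given survival to 5 years. At the earliest analysis it concerns early stoppers only.

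Two stronger readings are not supported. The 94% is not the chance of a missed cancer, because cases on treatment or within 30 days already enter the tables. Nor do the documents show that the plan would understate an ibrutinib effect: the number of cases outside the window is unknown and attribution is not possible. The primary endpoint, decision rule and power are untouched.

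**What to change.** Add to Section 16.325, in substance:

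> New primary malignancies (skin; non-skin solid; hematologic other than CLL or DLBCL) diagnosed from first dose to the data cut-off will be reported as number of patients, with type, time from first dose and from last dose, and whether other CLL therapy came first. The sources are the New Primary and adverse event forms. The table will be given at the final analysis and updated when event monitoring ends. The 30-day limit does not apply to malignancies.

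Also reconcile the 30-day sentence with Sections 4.0 and 18.1, by stating whether other adverse events recorded during Observation are tabulated and, if so, how. Cumulative incidence with death as a competing event is optional.

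The cost is one descriptive table and one later update, from forms already required. No visits, patients, alpha or power change. The toxicity profile may look slightly less favourable, and the table should say that a single-arm trial cannot assign cause.
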